# 5.0 Subject Disposition

The number of subjects in each of the following categories will be summarized by site and overall for each treatment arm and overall:

- Subjects who were screened;
- Subjects who were randomized;
- Subjects who took at least one dose of study drug;
- Subjects who completed protocol-specified treatment (ABBV-4083, albendazole, and the overall regimen [i.e., both study drugs]);
- Subjects who prematurely discontinued study drug (ABBV-4083, albendazole, and at least one of ABBV-4083 or albendazole);

- Subjects who completed the protocol-defined follow-up period;
- Subjects who prematurely discontinued study follow-up;
- Subjects in the PP population.

The number and percentage of subjects, overall and by treatment arm, who prematurely discontinued study drug (ABBV-4083, albendazole, and at least one of ABBV-4083 or albendazole) will be summarized by primary reason for discontinuing study drug (ABBV-4083 and albendazole) and overall for discontinuing at least one of ABBV-4083 or albendazole. The number and percentage of subjects, overall and by treatment arm, who prematurely discontinued the study will also be provided.

The number and percentage of subjects, overall and by treatment arm, who interrupted study drug (ABBV-4083, albendazole, and at least one of ABBV-4083 or albendazole) will be summarized by primary reason for interrupting study drug (ABBV-4083 and albendazole) and overall for interrupting at least one of ABBV-4083 or albendazole.

# 6.0 Study Drug Duration and Compliance

For the Safety population, duration of treatment will be summarized by treatment arm and overall. Duration of treatment is defined for each subject as last dosing date minus first dosing date + 1 day. Duration of treatment will be summarized using the number of subjects treated, mean, standard deviation, median, Q1, Q3, minimum, and maximum. In addition, the number and percentage of subjects by each treatment duration interval (1 to 7 days, 8 to 14 days, or > 14 days) will be summarized, and the number and percentage of subjects with duration long enough to meet the Per Protocol definition will also be summarized.

For the Safety population, treatment compliance will be summarized by treatment arm separately for ABBV-4083/matching placebo and albendazole/matching placebo. Treatment compliance is defined as the number of capsules that were taken divided by the number of capsules that should have been taken (56 capsules for 14 days of ABBV-4083/matching placebo at 400 mg QD, 42 capsules for 14 days of

ABBV-4083/matching placebo at 300 mg QD, 7 capsules for 7 days of albendazole/matching placebo). The mean, median, standard deviation, Q1, Q3, minimum, and maximum of treatment compliance will be summarized. In addition, the number and percentage of subjects with treatment compliance between 80% and 120% will also be summarized, excluding subjects with missing values in the denominator. A listing of each subject's treatment compliance will also be provided.

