## 4.0 Analysis Populations

The following population sets will be used for the analyses.

The Intention-to-Treat (ITT) population includes all randomised subjects who received at least one dose of study drug. The ITT population will be used for all non-primary efficacy estimands. Subjects will be included in the analysis according to the treatment arm to which they were randomised.

The Per-Protocol (PP) population will include all ITT subjects who had Month 6 nodulectomy (ND6M) with live female adult worms, who completed treatment and did not take prohibited medication(s) during the study. Treatment completion is defined as taking at least 6 out of 7 days of ABBV-4083 in Arm A, 12 out of 14 days of ABBV-4083 in Arm B, 6 out of 7 days of ABBV-4083 + albendazole in Arm C, 6 out of 7 days of ABBV-4083 and all 3 days of albendazole in Arm D, and 6 out of 7 days of albendazole in Arm E. Prohibited medications (Appendix B) include those with anti-filarial or anti-*Wolbachia* effect taken at any time during the study, or strong CYP3A inducers or dexamethasone taken during the treatment period. The PP population will be used as the primary population for testing the two primary hypotheses (Section 2.1).

The Safety population includes all randomized subjects who received at least one dose of study drug. Subjects will be included in the analysis according to treatment as randomized. The Safety population is the same as the ITT population.

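### SAP 6.0 counts subjects with enough duration for the per-protocol definition from a date span, and its compliance rate mixes each drug with its own placebo; neither shows active days taken

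*SAP*

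**What the plan says.** SAP 6.0 works on the Safety population. Its duration variable is a single span per subject: "Duration of treatment is defined for each subject as last dosing date minus first dosing date + 1 day". From that variable it plans a per-protocol line: "the number and percentage of subjects with duration long enough to meet the Per Protocol definition will also be summarized".

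Compliance is capsules taken divided by capsules due, reported "separately for ABBV-4083/matching placebo and albendazole/matching placebo". The denominators are "56 capsules for 14 days of ABBV-4083/matching placebo at 400 mg QD" (42 at 300 mg) and "7 capsules for 7 days of albendazole/matching placebo". SAP 6.0 adds that "the number and percentage of subjects with treatment compliance between 80% and 120% will also be summarized".

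SAP 4.0 defines treatment completion differently, by days of the assigned active drug: 6 of 7 in Arms A, C and E, 12 of 14 in Arm B, and "6 out of 7 days of ABBV-4083 and all 3 days of albendazole in Arm D".

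Under SAP 2.3 all arms take ABBV-4083 or its placebo for 14 days. In Arms A, C and D the second week is placebo, and in Arm E all 14 days are. Albendazole capsules are taken for 7 days. They are all active in Arms C and E, 3 active and 4 placebo in Arm D, and all placebo in Arms A and B.

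**The concern.** The duration line claims to show who had enough treatment for the per-protocol rule, but its variable does not contain the quantity that the rule uses. A span cannot see a gap, and one span per subject cannot test two drug-specific thresholds, as Arm D requires. Gaps are foreseen: Protocol 6.5.2 lets interrupted treatment resume, SAP 5.0 tabulates interruptions, and SAP 6.0 has a category above 14 days. An interruption that is later resumed lengthens this duration.

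The compliance rate has a separate problem. Where a drug's denominator contains placebo, placebo capsules can offset missed active ones, so a subject can be in band while failing completion.

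At stake is the description of how much active drug each arm received. The arms differ mainly in active days (7 or 14 of ABBV-4083; 0, 3 or 7 of albendazole), yet a fully dosed subject in any arm would show a duration of 14.

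**Working it through.** **Plan's own denominators.** Protocol 7.3.1.2 gives 4 ABBV-4083 or placebo capsules a day for 14 days and 1 albendazole or placebo capsule a day for 7 days. So 14 × 4 = 56; at 300 mg, 14 × 3 = 42; albendazole 7 × 1 = 7. All three figures in SAP 6.0 are reproduced.

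**Duration** = last date − first date + 1.
- Doses on Day 0 and Day 13: 13 − 0 + 1 = 14 days in every arm, whatever was missed between.
- Active dates only, doses on Day 0 and Day 6: 6 − 0 + 1 = 7 days, with 2 of 7 doses taken. Dropping placebo dates therefore does not repair the measure.
- Arm B has no ABBV-4083 placebo and has the same gap, so the span is a cause in its own right.

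SAP 6.0 states no cut-off for long enough. If the cut-offs are taken as 6 days (12 in Arm B), the error runs one way: a span is never shorter than the number of days dosed, so the line can overstate completion but not understate it.

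**Compliance** = capsules taken / capsules due. Below, whole active days are missed and all placebo is taken.

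| Arm and drug | Active days missed | SAP 6.0 compliance | Active-only | SAP 4.0 threshold for that drug |
|---|---|---|---|---|
| A, C, D: ABBV-4083 | 1 | 52/56 = 92.9%, in band | 6/7 = 85.7% | met |
| A, C, D: ABBV-4083 | 2 | 48/56 = 85.7%, **in band** | 5/7 = 71.4% | **failed** |
| A, C, D: ABBV-4083 | 3 | 44/56 = 78.6%, out | 4/7 = 57.1% | failed |
| D: albendazole | 1 | 6/7 = 85.7%, **in band** | 2/3 = 66.7% | **failed** |
| D: albendazole | 2 | 5/7 = 71.4%, out | 1/3 = 33.3% | failed |
| C, E: albendazole | 1 | 6/7 = 85.7%, in band | 6/7 = 85.7% | met |
| C, E: albendazole | 2 | 5/7 = 71.4%, out | 5/7 = 71.4% | failed |
| B: ABBV-4083 | 2 | 48/56 = 85.7%, in band | 12/14 = 85.7% | met |
| B: ABBV-4083 | 3 | 44/56 = 78.6%, out | 11/14 = 78.6% | failed |

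Masking occurs in two places only: ABBV-4083 in Arms A, C and D, and albendazole in Arm D. At 300 mg the ABBV-4083 result is the same (36/42 = 85.7%).

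If single capsules could be missed, the lowest in-band count is 45/56 = 80.4%, which with all 28 placebo capsules leaves 17/28 = 60.7% of active drug. At 300 mg it is 34/42 = 81.0%, leaving 13/21 = 61.9%.

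The reverse also happens. A subject in Arm A who takes all 7 active days and stops after Day 9 has 10 × 4 = 40 capsules, 40/56 = 71.4%, out of band, but meets the completion threshold.

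**The case against.** The best defence is that nothing inferential rests on SAP 6.0. Per-protocol membership comes from SAP 4.0, and SAP 9.3.2 tests in that population. SAP 5.0 separately counts completion of each drug and of the regimen, with discontinuations and interruptions. Protocol 7.6 has every intake observed and recorded, and drug levels measured in blood. All of that stands and limits the point. It does not make the duration line right: the SAP 5.0 completion count cites no SAP 4.0 threshold, and its per-protocol count also depends on nodulectomy, live worms and prohibited medication.

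It is also fair that capsule adherence to a blinded 14-day course is a legitimate measure. The subject who stops after Day 9 did not adhere to it. That is a reason to keep the all-capsule figure and label it as such.

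A reader might infer more than the documents support:
- That compliance is masked in all four 7-day arms. It is not in Arm E, whose only active drug has an all-active denominator; 5/7 = 71.4% falls out of band. The albendazole figure in Arm C is likewise sound.
- That the two drugs are pooled with each other. SAP 6.0 reports them separately; pooling is only of a drug with its own placebo.
- That Part 2 regimens are chosen on these tables. Protocol 10.9 bases selection on all available data and names safety, tolerability, *Wolbachia* depletion and embryogenesis; it does not name compliance or duration.
- That a difference between the SAP 6.0 count and the per-protocol count is an error in itself. The two should differ, since the per-protocol population has further conditions.

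**Conclusion.** Wrong as written, and minor. The duration line cannot show who met the SAP 4.0 thresholds in any arm. The compliance band hides a completion failure in a narrow window: with whole days missed and all placebo taken, exactly 2 missed ABBV-4083 days in Arms A, C or D, or 1 missed active albendazole day in Arm D.

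The effect is confined to descriptive exposure tables. The documents give no expected rate of missed doses, so the number of subjects affected cannot be stated; observed dosing suggests that it would be small. The 14-day duration example assumes that placebo dosing dates count as dosing dates, which SAP 6.0 does not say, but the measure fails without that assumption too. The 61% figures need part-doses, which are less plausible when staff observe each intake.

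**What to change.** 1. Base the per-protocol line in SAP 6.0 on active days taken, per drug, against the SAP 4.0 thresholds for the arm, in place of the date span.
2. Add active-drug compliance where active drug is assigned. For ABBV-4083 the denominators are 28 capsules in Arms A, C and D and 56 in Arm B (21 and 42 at 300 mg). For albendazole they are 3 in Arm D and 7 in Arms C and E. Show not applicable for ABBV-4083 in Arm E and for albendazole in Arms A and B, where no active capsules are assigned and the ratio is undefined.
3. Keep the all-capsule rate, labelled as adherence to the blinded regimen.

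The cost is a few lines of SAP text and one derived variable, built after unblinding from the intake already recorded in the eCRF and the randomisation code. No new data are needed and no test changes.

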# 7.0 Demographics, Baseline Characteristics, Medical History, and Prior/Concomitant Medications

Demographics, baseline or disease characteristics, medical history, and prior and concomitant medications will be summarized for the PP and ITT populations by treatment arm as well as overall. Categorical variables will be summarized with the number and percentage of subjects; percentages will be calculated based on the number of non-missing observations. Continuous variables will be summarized with descriptive statistics (number of non-missing observations, mean and standard deviation, median, Q1, Q3, minimum and maximum).

#### 7.1 Demographics and Baseline Characteristics

Continuous demographic variables include age, weight, height, and body mass index (BMI). Categorical demographic variables include sex, race, age (< 40, or  $\ge$  40 years), weight (< 60 or  $\ge$  60 kg), and BMI (< 18, 18 to < 25, or  $\ge$  25 kg/m^2).

Baseline characteristics include symptoms of onchocerciasis disease (ocular or skin), number of operable sites with onchocercomata (continuous and categorical: 0, 1 or > 1), number of palpated nodules (continuous and categorical: 0, 1 or > 1), skin microfilarial density (continuous and categorical:  $\leq 5$  or > 5 mf/mg), district of residence (Kimpese, Masa, Masi-Manimba, Moanza, Nsonampangu, Pay Kongila, or Other), number of years resident in endemic area (continuous), number of previous ivermectin rounds (continuous and categorical 0, 1, or > 1), time since the last ivermectin administration (continuous and categorical,  $\leq 1$  year or > 1 year), parasitological co-infections (e.g., *Loa loa* or *Schistosoma haematobium*). Baseline continuous laboratory values include aspartate aminotransferase (AST), alanine aminotransferase (ALT), alkaline phosphatase (AP), creatinine clearance, estimated glomerular filtration rate (eGFR), total bilirubin, and albumin.

"Baseline" refers to the last non-missing observation before the first administration of study drug.

#### 7.2 Medical History

Medical history data will be coded using the Medical Dictionary for Regulatory Activities (MedDRA). The actual version of the MedDRA coding dictionary will be noted in the statistical tables and clinical study report. The number and percentage of subjects in each medical history category (by MedDRA system organ class and preferred term) will be summarized overall and by treatment arm. The system organ class (SOC) will be presented in alphabetical order, and the preferred terms will be presented in alphabetical order, system organ class (SOC) will be counted only once in each row (SOC or preferred term).

#### 7.3 Prior and Concomitant Medications

Prior and concomitant medications will be summarized by generic name. A prior medication is defined as any medication taken prior to the date of the first dose of study drug. A concomitant medication is defined as any medication that started prior to the date of the first dose of study drug and continued to be taken after the first dose of study drug or any medication that started on or after the date of the first dose of study drug, but not after the date of the last dose of study drug. The number and percentage of subjects taking medications will be summarized by generic drug name based on the World Health Organization (WHO) Drug Dictionary for both prior and concomitant medications. Anthelmintic medications taken prior to the initiation of study drug will not be included in the summary of concomitant medications.

#### 8.0 Handling of Potential Intercurrent Events for the Primary Endpoint

The primary efficacy endpoint (defined in Section 3.1) will be analyzed in the PP and ITT populations and the following methods will be used to address potential intercurrent events:

- Subjects who did not complete treatment will be excluded from the PP population (definition of completion in Section 4.0). They will be included in the ITT population.
- Subjects who took prohibited medications (Appendix B) will be excluded from the PP population. They will be included in the ITT population, but subjects who took medications with an anti-filarial or anti-*Wolbachia* effect at any time during the study will be counted as failures in the ITT population (Section 9.2).
- Subjects who withdrew due to a safety issue (premature discontinuation of study or study treatment due to an adverse event related to either study drug) will be excluded from both the PP population and the ITT population analyses if they have no count of live female adult worms (no ND6M results or no live female adult worms in the ND6M results). If the subjects had live female adult worms in the ND6M results, they will be included in both the PP population and the ITT population analyses with any missing *Wolbachia* depletion results imputed as failures (Section 9.2).
- Subjects who prematurely discontinued from the study or study treatment for reasons independent of the treatment (for example, lost to follow-up, withdrew informed consent, or due to an adverse event not related to either study drug) will be excluded from both the PP population and the ITT population analyses if they have no count of live female adult worms (no ND6M results or no live female adult worms in the ND6M results). If the subjects had live female adult worms in the ND6M results, they will be included in the PP population analysis if not all *Wolbachia* depletion results were missing and they will be included in the ITT population analysis with any missing *Wolbachia* depletion results imputed through multiple imputation (Section 9.2).

# 9.0 Efficacy Analyses

#### 9.1 General Considerations

The analyses for the primary endpoint will be conducted in both the PP population and the ITT population. However, the PP population will be the population used for the primary estimand comparisons. All other efficacy analyses will be conducted in the ITT population. The testing of the two primary hypotheses will be 2-sided at an alpha level of 0.10. No adjustment for multiple comparisons will be made.

The Primary Analysis will be performed after all subjects have completed the Month 6 Visit or have prematurely discontinued study follow-up. This will be the only and final analysis for the primary endpoint as well as all other efficacy endpoints.

If Arm A, B, C, or D is closed and then reopened using ABBV-4083 at 300 mg QD, only the new arm using 300 mg ABBV-4083 will be included in the efficacy analyses of this SAP. Efficacy summaries of the closed arms may be performed as ad hoc analyses.

#### 9.2 Handling of Missing Data for the Primary Endpoint

First, subjects with no count of live female adult worms (no ND6M results or no live female adult worms in the ND6M results) will be excluded from the PP population and the ITT population analysis, because the primary endpoint is a worm-level endpoint about the *Wolbachia* status of a live female adult worm in the ND6M results.

Then, if a subject took prohibited medications with an anti-filarial or anti-*Wolbachia* effect (Appendix B) at any time during the study, all live female adult worms in that subject will be counted as having *Wolbachia* for the ITT population analyses, regardless of the observed *Wolbachia* status. All worms in such subjects will be excluded according to the definition of the PP population (Section 4.0).

Then, if a subject withdrew due to a safety issue (Section 8.0), all the live female adult worms that have missing *Wolbachia* status will be imputed as having *Wolbachia* for both

the PP population and the ITT population analyses. Any live female adult worm that has the observed *Wolbachia* status will be analyzed as observed.

Finally, if any live female adult worm still has missing *Wolbachia* status, the *Wolbachia* status will be imputed for the worms of those subjects in the ITT population analyses using the multiple imputation described below, but those worms will be excluded from the analyses for the PP population.

For multiple imputation, the missing *Wolbachia* depletion results will be generated in 30 datasets in SAS PROC MI (fully conditional specification). The logistic regression method will be used to impute the binary primary *Wolbachia* status for each live female adult worm with missing *Wolbachia* status. The imputation model will include treatment and the randomization stratification factor (Section 2.3) as covariates. The random seed for PROC MI will be the SAS numerical form of the first subject randomization date in the study. In case of non-convergence, the random seed will be updated by adding 100,000 at each attempt until convergence of model occurs. If the model will not converge due to data sparsity issue, the randomization stratification factor will be removed from the imputation model. The primary endpoint data from the 30 datasets will then be separately analyzed using the method described in Section 9.3.1. The results will be combined using SAS PROC MIANALYZE to generate the final inference.

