10.4 Handling of Potential Intercurrent Events for the Primary and Key Secondary Endpoints

Subjects who do not complete the treatment as defined above will be excluded from the PP populations (but will be included in the ITT analyses). Subjects in Part 2 with evidence of reinfection will be included in all analyses as it is not possible to distinguish between reinfection and a failure in this study. However, in sensitivity analyses, those subjects will be excluded from efficacy analysis. Subjects in Part 2 who do not have skin snips at Month 24 will be excluded from the PP for microfilaria population, except those who received ivermectin rescue before Month 24. Any subject who received ivermectin rescue before Month 24 as allowed per protocol will be counted as a failure in both the PP and ITT analyses of the Part 2 primary and key secondary endpoints. Subjects who do not have nodulectomy data at Month 6 (for Part 1 and for Part 2 Alternate Scenario) or Month 24 (for Part 2) will be excluded from the PP for the ND6M or ND24M populations, respectively. Subjects who take prohibited medications (see Appendix 8-sections II and IV) will be excluded from the PP analyses; subjects who take medications with an anti-filarial or anti-Wolbachia effect at any time during the study (see Appendix 8 - Section II) will be counted as failures in the ITT analyses.

In the ITT analysis of the primary and key secondary endpoints, if the result is missing for the assessment, the assessment of that outcome will be a failure if the absence of data is due to administration of prohibited medication or withdrawal due to efficacy or safety issue. In the event of withdrawal of informed consent, subject lost to follow-up or withdrawal for a reason independent from the treatment (e.g. moving, lethal accident), multiple imputation will be used to impute the missing data.

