#### 2.4 Sample Size Determination

To test the primary hypothesis for the proof of concept, an alternating logistic regression will be used to compare the proportion of live female adult worms without *Wolbachia* at Month 6 between each of the four active arms (Arm A, B, C, or D) and the control arm (Arm E), taking into account the clustering of this worm-level endpoint by subject. Using simulations that add substantial clustering by subject to the endpoint values and assuming the number of worms in each subject varies from 1 to 10, following the multinomial distribution with probability = (0.20, 0.16, 0.16, 0.16, 0.08, 0.08, 0.08, 0.03, 0.03, 0.02) for values (1, 2, 3, 4, 5, 6, 7, 8, 9, 10), 17 subjects will provide 88% power to detect the difference between an active arm (Arm A, B, C, or D) where 70% of worms are without *Wolbachia* (2-sided  $\alpha = 0.10$ ). The clustering of the endpoint values by subject is provided by the Pearson intraclass correlation coefficient (ICC) for binary outcomes and was given as ICC = 0.54 for simulated arms where 70% or 30% of the worms are without *Wolbachia*.

To test the primary hypothesis for the combination rule, an alternating logistic regression will be used to compare the proportion of live female adult worms without *Wolbachia* at Month 6 between the combination arm (Arm C or D) and the two single drug arms (Arm A and E) separately, 25 subjects per arm will provide 81% power to detect the difference between the combination arm where 90% of worms are without *Wolbachia* and the single drug arm where 70% of worms are without *Wolbachia* (2-sided  $\alpha = 0.10$ ). ICC = 0.54 was added to the simulated arm where 70% of the worms are without *Wolbachia*. Minimal clustering (ICC = 0.01) was added to the simulated arm where 90% of the simulated arm where 90% of the worms are without *Wolbachia* because there would be little variation among subjects with an overall high response rate. 30 subjects will be enrolled per arm to account for 17% drop out by Month 6.

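### SAP 8.0 and 9.2 leave dosed subjects with no Month 6 nodulectomy result out of the Part 1 ITT analysis, where protocol 10.4 gives failure or imputation rules, and SAP 13.0 does not list the difference

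*SAP*

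**What the plan says.** **ITT set.** SAP 4.0: "The Intention-to-Treat (ITT) population includes all randomised subjects who received at least one dose of study drug".

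**SAP rule for missing Month 6 data.** Under SAP 9.2, subjects without a worm count, whether because there is no nodulectomy result or because no live female worm was found, "will be excluded from the PP population and the ITT population analysis, because the primary endpoint is a worm-level endpoint". SAP 8.0 says the same of subjects who leave for a drug-related safety reason and of those who leave for reasons unrelated to treatment: they "will be excluded from both the PP population and the ITT population analyses if they have no count of live female adult worms". Failure imputation and multiple imputation then act only on worms that were found but have no *Wolbachia* status.

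**Protocol rule.** Under protocol 10.4, subjects without nodulectomy data "will be excluded from the PP for the ND6M or ND24M populations, respectively". For the ITT analysis of the primary endpoint, an outcome with a missing result "will be a failure if the absence of data is due to administration of prohibited medication or withdrawal due to efficacy or safety issue". After consent withdrawal, loss to follow-up or another unrelated reason, "multiple imputation will be used to impute the missing data".

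**Role of the ITT analysis.** SAP 9.3.3 gives the ITT rerun as the only supplementary analysis of the primary endpoint.

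**Declaring departures.** SAP 1.0 says that analyses match the protocol unless Section 13.0 notes otherwise. The 13.0 entry for Sections 8.0 and 9.2 says only that the conditions for imputation were clarified.

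**Imputation model for found worms.** SAP 9.2: "The imputation model will include treatment and the randomization stratification factor (Section 2.3) as covariates". In SAP 2.4 the planned within-subject clustering "was given as ICC = 0.54 for simulated arms where 70% or 30% of the worms are without" *Wolbachia*, and 0.01 for the 90% arm.

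**The concern.** A reader will look to the ITT rerun for reassurance that the PP result does not depend on who was lost. It cannot give that. The rerun differs from PP only through subjects who do have live female worms at Month 6: those who did not complete treatment, those who took prohibited medication, and those with some worms of unknown status. Subjects with no nodulectomy result are absent from both analyses, although the SAP's own ITT definition includes them and protocol 10.4 has rules for them.

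The plan expects 17% drop-out by Month 6. If loss were related to outcome, or differed in kind between arms, both odds ratios could be biased in the same way and still agree.

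A smaller, separate point concerns found worms with missing status. The model imputes each from arm and stratum alone and ignores the other worms in the same subject, although the plan assumes strong within-subject correlation in the 30% and 70% arms.

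**Working it through.** **1. The planned loss.** Protocol 10.3.1 and SAP 2.4 need 25 analysed subjects per arm and allow for 17% drop-out: 25 / 0.83 = 30.1, planned as 30. The loss is 5 per arm (5/30 = 16.7%), about 25 of 150 overall. The stated powers are also reproducible with beta-binomial worms and a robust logit Wald test in place of alternating logistic regression: 88.6% with exchangeable weights for 17 per arm (plan 88%), and 81.1% with independence weights for 25 per arm (plan 81%). No single weighting matched both.

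**2. Inputs for the illustration.** Arm C 90% and Arm A 70% of worms clear; 30 dosed and 25 with a result per arm; lost subjects carry the planning worm counts. Their mean is 0.20×1 + 0.16×(2+3+4) + 0.08×(5+6+7) + 0.03×(8+9) + 0.02×10 = 3.79, with no zeros. Planned odds ratio: (0.90/0.10) / (0.70/0.30) = 9 / 2.333 = **3.86**.

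**3. Ordinary loss under protocol 10.4.** Multiple imputation from arm and stratum gives lost subjects their arm's rate. C: (22.5 + 5×0.9)/30 = 90%. A: (17.5 + 5×0.7)/30 = 70%. The expected odds ratio stays at about 3.86, so this part of the protocol rule cannot reveal informative loss.

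**4. Losses counted as failures under protocol 10.4.** With k of 30 lost, the rate is the arm rate × (30 − k)/30.

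| k | Rate C | Rate A | OR, losses in C only | OR, k in each arm | OR, losses in A only |
|---|---|---|---|---|---|
| 2 | 84.0% | 65.3% | 2.25 | 2.79 | 4.78 |
| 5 | 75.0% | 58.3% | 1.29 | 2.14 | 6.43 |

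This part would move the ITT result, but such losses may be few: protocol 6.5.2 keeps subjects who stop study drug in follow-up.

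**5. Informative ordinary loss, which neither document tests.** With clearance rate q in the lost subjects, C = (22.5 + 5q)/30 and A = (17.5 + 5q)/30. The values of q are assumptions.

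| q in C | q in A | Rates C, A | OR |
|---|---|---|---|
| 0.6 | 0.7 | 85.0%, 70.0% | 2.43 |
| 0.5 | 0.5 | 83.3%, 66.7% | 2.50 |
| 0.9 | 0.5 | 90.0%, 66.7% | 4.50 |
| 0 | 1 | 75.0%, 75.0% | **1.00** |
| 1 | 0 | 91.7%, 58.3% | **7.86** |

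In a simulation (1,000 trials, 30 imputations, a generalised estimating equation in place of alternating logistic regression), the median pooled p was 0.108, 0.093 and 0.004 for the first three rows, against 0.009 when lost subjects follow their arm. The test level is 0.10. The stand-in was slightly optimistic on power (85% where the plan states 81%).

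For A versus E (70% vs 30%, odds ratio 5.44), counting 5 losses per arm as failures gives 58.3% vs 25.0%, odds ratio 4.20. The worst case is 58.3% vs 41.7%, odds ratio 1.96.

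**6. Imputing found worms.** Beta-binomial with S = (1 − ICC)/ICC. For a 70% arm with ICC 0.54, S = 0.46/0.54 = 0.852 and 0.7 × S = 0.596. Given two other observed worms, the chance that the missing one is clear is 0.596/2.852 = 21% if neither is clear and 2.596/2.852 = 91% if both are. The SAP model gives about 70% either way, apart from stratum. For a 90% arm with ICC 0.01, S = 99 and 0.9 × S = 89.1: 89.1/101 = 88% and 91.1/101 = 90%, so little is lost there.

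**The case against.** **A worm-level endpoint has no unit without a worm.** The SAP says so openly, and protocol 10.4 does not say how many worms a missing subject contributes. This justifies leaving out subjects who were operated on and had no live female worm. For subjects with no nodulectomy it explains the SAP's choice but does not reconcile it with the protocol.

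**Protocol 10.4 does not expressly keep these subjects in ITT.** It does so for non-completers, but its sentence on missing nodulectomy data has no such clause. The inference rests on the following paragraph, which sets ITT rules for missing primary-endpoint results and names loss to follow-up and consent withdrawal. That is the natural reading, though not an explicit one.

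**Following the protocol would not solve the problem.** This stands. A reader might infer that the exclusion alone stops ITT from detecting biased loss. Step 3 shows otherwise: for ordinary loss, the protocol's imputation with the SAP's model would reproduce the arm rates. A missing-not-at-random analysis would be an addition to both documents, not the restoration of a promised one.

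**Two further inferences go too far.** One is that Section 13.0 presents this departure as a clarification. That table describes changes between SAP versions, and version 1.0 is not available, so the exclusion may have been there already. The other is that all 17% would lack a result. The Part 1 schedule (protocol Appendix 1) appears to include nodulectomy at Early Termination, and the SAP does not say whether such nodules count as Month 6 results.

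**Loss will be visible.** Discontinuation by arm (SAP 5.0), baseline tables for PP and ITT (7.0) and a deviation listing that covers nodulectomy not performed (Appendix A) will show it. They show that loss occurred, not what it does to the odds ratio.

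**The imputation point is narrow.** It has no bearing on subjects with one worm (20% in the planning distribution), and the number of found worms with missing status is unknown.

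**Conclusion.** The concern holds in a limited form. The SAP and protocol 10.4 do not align for dosed subjects without a Month 6 nodulectomy result, and Section 13.0 does not say so. These subjects enter neither the primary analysis nor its only supplementary analysis, so agreement between the two carries no information about bias from their loss.

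The size of any bias is unknown, because the documents give neither the reasons for loss nor their split by arm. The bounds of 1.00 to 7.86 around 3.86 for C versus A are extremes. They assume the full planned loss in both arms, no nodulectomy result for any lost subject, and the same worm counts in lost subjects as in the rest; effects shrink if some would have had no live female worm.

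The PP test remains primary, and no passage makes the choice of Part 2 scenario depend on ITT. This is an inexpensive improvement that should be made, not a flaw in the primary test.

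**What to change.** 1. **Record and label.** Enter the difference from protocol 10.4 in SAP 13.0, label the current ITT rerun 'observed worms', and state whether nodules taken at Early Termination count as Month 6 results.
2. **Add one sensitivity analysis in SAP 9.3.3** that keeps dosed subjects with no nodulectomy result. Draw their worm counts from the observed Month 6 counts in the same arm, zeros included. Set their worms to with *Wolbachia* for the failure reasons in protocol 10.4 and impute the rest. Vary the imputed clearance rate separately by arm as a tipping-point analysis, so that informative loss is tested in either direction. Report subjects who had a nodulectomy but no live female worm by arm, not as missing.
3. **Improve the imputation model for found worms** by adding the subject's other observed worm results or a subject random effect. Keep the current model as the fallback for non-convergence or when the subject has no other worm.

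The cost is SAP wording, some extra programming and a worm-count assumption that cannot be checked for lost subjects. ITT estimates may look less favourable. No new data are needed, and the primary PP test does not change.
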